#### 1. Serious adverse events

A serious adverse event (SAE) is any untoward medical occurrence that at any dose:

- Results in death
- Is life-threatening (defined as an event in which the subject was at risk of death at the time of the event; it does not refer to an event which hypothetically might have caused death if it were more severe)

## Clinical Study Protocol

- Requires inpatient hospitalization or causes prolongation of existing hospitalization (see NOTE below)
- Results in persistent or significant disability/incapacity
- Is a congenital anomaly/birth defect
- Is an important medical event (defined as medical event(s) that may not be immediately life-threatening or result in death or hospitalization but, based upon appropriate medical and scientific judgment, may jeopardize the subject or may require intervention [e.g., medical, surgical] to prevent one or the other serious outcomes listed in the definition above.) Examples of such events include, but are not limited to, intensive treatment in an emergency room or at home for allergic bronchospasm, blood dyscrasias or convulsions that do not result in hospitalization.) Potential drug induced liver injury (DILI) is also considered an important medical event. (See section 6 for the definition of potential DILI.)

Suspected transmission of an infectious agent (e.g., pathogenic or nonpathogenic) via the study drug is an SAE.

### NOTE:

The following hospitalizations are not considered SAEs:

- A visit to the emergency room or other hospital department <24 hours that does not result in admission (unless considered an important medical or life-threatening event)
- Elective surgery, planned prior to signing consent
- Admissions as per protocol for a planned medical/surgical procedure
- Routine health assessment requiring admission for baseline/trending of health status (e.g., routine colonoscopy)
- Medical/surgical admission other than to remedy ill health and planned prior to entry into the study. Appropriate documentation is required in these cases.
- Admission encountered for another life circumstance that carries no bearing on health status and requires no medical/surgical intervention (e.g., lack of housing, economic inadequacy, caregiver respite, family circumstances, administrative reason).

### 1A. Serious adverse event collection and reporting

Following the subject's written consent to participate in the study, all SAEs, whether related or not related to the study drug, must be collected, including those thought to be associated with protocol-specified procedures. All SAEs must be collected that occur during the screening period and within 30 days of discontinuation of dosing. The investigator should report any SAE that occurs after these time

periods and that is believe to be related to study drug or protocol-specified procedure. All SAEs must be reported immediately to the Woman's Hospital Foundation Institutional Review Board at [contact], Woman's Health Research Institute at [contact] and LSUHSC Institutional Review Board. SAEs must be recorded on an SAE Report Form or similar form (e.g., CIOMS, MedWatch). Reports are to be transmitted via email or confirmed facsimilie (fax) transmission.

In cases where the investigator learns of the SAE after its occurrence and resolution, the time and circumstances of the event will be recorded. The reporting requirements will still be followed

All SAEs should be followed to resolution or stabilization.

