### **STUDY PLANS AND PROCEDURES:**

Prospective, randomized controlled trial

All patients with diagnosed previable preterm premature rupture of membranes (PPROM), greater than 18 years old, with gestational age between 18 0/7 and 22 6/7 will be admitted to Woman's Hospital's Labor and Delivery unit for a 24-hour observation period. Rupture of membranes will be diagnosed by history and physical exam findings which include either/or 1) visualization of amniotic fluid passing from the cervical canal and pooling in the vagina via sterile speculum examination, 2) a basic pH (i.e., positive nitrazine) test of vaginal fluid, 3) arborization (ferning) of dried vaginal fluid identified via microscopic examination, or 4) an amniotic fluid index (AFI) of less than 4cm. A standard set of blood and imaging tests will be ordered prior to admission, to include a complete blood cell count and ultrasound imaging of the fetus. Patients will then be admitted to Woman's Hospital Labor and Delivery unit for a 24-hour observation period. If, following the 24-hour observation period, there are no clinical signs of preterm contractions/labor, active genitourinary tract infection, vaginal bleeding, fever, or pelvic pain, then the patient will be randomized into either the control group (i.e., the group not receiving antibiotics) or the treatment group (i.e., the group receiving antibiotics). Randomization will be performed by computer-generated numbering by sampling  $\frac{N}{2}$  patient ID numbers from 1 to  $N$  without replacement using the `sample()` function in R statistical software.

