### Treatment Regimen

Patients randomized into the treatment (antibiotic) arm of the study will be treated with a seven-day course of oral azithromycin and amoxicillin. Azithromycin will be dosed as single 500 mg dose immediately following randomization, yet prior to discharge to home, followed with 250mg each day for 4 more days. Amoxicillin will be dosed as 500mg orally three times daily for 7 days with its first dose also being given prior to discharge home.

Due to delayed result reporting for chlamydia, gonorrhea and trichomonas within the Woman's Hospital Laboratory, results of such testing will not be available at the time of randomization. Those pa-

tients testing positive for any of the aforementioned genitourinary infections will be treated according to standard guidelines.

Inclusion Criteria:

1. Singleton gestation
2. Gestational age of greater than 18 0/7 but less than or equal to 22 6/7
3. Diagnosis of prelabor premature rupture of membranes as determined by clinical examination noting either/or 1) visualization of amniotic fluid passing from the cervical canal and pooling in the vagina via sterile speculum examination, 2) a basic pH (i.e., positive nitrazine) test of vaginal fluid, 3) arborization (ferning) of dried vaginal fluid identified via microscopic examination, or 4) an amniotic fluid index (AFI) of less than 4cm.
4. Greater than or equal to 18 years of age
5. Those with no known drug allergies or significant adverse reactions to azithromycin or amoxicillin
6. Afebrile at the time of presentation and throughout 24-hour observation period
7. Patient must be able to provide informed consent

Exclusion Criteria:

1. Fetal anomalies
2. Diabetes mellitus, including both pre-gestational and gestational
3. Abnormal placentation
4. Poor dating with dating ultrasound performed later than or equal to 20 0/7 weeks
5. Current subchorionic hemorrhage or current vaginal bleeding on presentation
6. Hypertensive disease, including pre-gestational chronic hypertension, gestational hypertension and pre-eclampsia/eclampsia
7. History of amniocentesis during this pregnancy
8. History of cervical incompetence, history of cerclage in previous pregnancy or current cerclage in place
9. Current documented urinary tract infection or bacteriuria
10. Current documented genital tract infection (Chlamydia, gonorrhea, or trichomonas)

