### **Adverse Event Procedures**

An adverse event (AE) is defined as any new untoward medical occurrence or worsening of a preexisting medication condition in a clinical investigation subject administered an investigational (medicinal) product and that does not necessarily have a causal relationship with this treatment. An AE can therefore be any unfavorable and unintended sign (such as an abnormal laboratory findings), symptom, or disease temporarily associated with the use of investigational products, whether or not considered related to the investigational product.

The causal relationship to study drug is determined by a physician and should be used to assess all adverse events (AEs). The causal relationship can be one of the following

- Related: There is a reasonable causal relationship between the study drug administration and the AE.
- Not related: There is not a reasonable causal relationship between study drug administration and the AE.

The term “reasonable causal relationship” means there is evidence to suggest a causal relationship.

Adverse events can be spontaneously reported or elicited during open-ended questioning, examination, or evaluation of a subject. (In order to prevent reporting bias, subjects should not be questioned regarding the specific occurrence of one or more AEs.)

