### 2A. Nonserious Adverse Event Collection and Reporting

The collection of nonserious AE information should begin at initiation of study drug. Non-serious AE information should also be collected from the start of a placebo lead-in period or other observational period intended to establish a baseline status for the subjects.

Nonserious AEs should be followed to resolution or stabilization, or reported as SAEs if they become serious (see Section 1A). Follow-up is also required for nonserious AEs that cause interruption or discontinuation of study drug and for those present at the end of study treatment as appropriate. All identified nonserious AEs must be recorded and described on the nonserious AE page of the CRF.

Completion of supplemental CRFs may be requested for AEs and/or laboratory abnormalities that are reported/identified during the course of the study.

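### All-cause SAE collection ends 30 days after dosing stops, an anchor only the antibiotic arm has, so collection windows differ by arm and conflict with continuous safety follow-up of all subjects

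*Protocol*

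**What the plan says.** Section 1A (Serious adverse event collection and reporting) opens with a general duty: after written consent, "all SAEs, whether related or not related to the study drug, must be collected". The next sentence bounds it: "All SAEs must be collected that occur during the screening period and within 30 days of discontinuation of dosing". Beyond that, the investigator should report only an SAE arising after these "periods and that is believe to be related to study drug or protocol-specified procedure".

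Under Treatment Regimen, azithromycin starts with a "single 500 mg dose immediately following randomization", and "Amoxicillin will be dosed as 500mg orally three times daily for 7 days". Study drug therefore lasts seven days in the treated arm. Study Plans and Procedures gives the control arm no antibiotics, and no placebo is described. Statistical Methods and Sample Size Calculations assigns 17 women to each arm. Study Rationale states that the trial is not blinded.

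Methods provides weekly outpatient visits to 23 0/7 weeks, then readmission and inpatient care until delivery. Reaching 34 0/7 is itself a reason for delivery.

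Two other places bear on who is followed and for how long:
- Adverse Event Procedures defines an adverse event as an occurrence in a "clinical investigation subject administered an investigational (medicinal) product".
- Ethical and Regulatory Requirements treats everyone who enters the study as evaluable for safety, wants all adverse events documented and reported to both review boards, and has adverse events evaluated continuously for as long as the patient is on study.

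**The concern.** The end of full SAE collection hangs on an event that occurs in one arm only. A treated woman has a definite stop date; a control does not. SAE counts by arm would then cover different lengths of follow-up, and a comparison of them would mix a drug effect with a difference in observation time.

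The treated stop date also falls well before the latest possible delivery. The time outside the window belongs to the longest latencies, which is the effect the trial hopes to produce. Ethical and Regulatory Requirements itself names harms of prolonged latency, among them intraamniotic infection, endometritis, abruption and retained placental products. When such an event meets the SAE definition late in a treated pregnancy, section 1A requires a report only if someone who knows the arm believes it related to the drug or to a procedure. Staff cannot follow that rule and also report every adverse event for as long as the woman is on study.

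**Working it through.** **Inputs.** Dosing starts at randomisation and lasts 7 days (Treatment Regimen). Collection continues for 30 days after dosing stops (section 1A). Entry is from 18 0/7 to 22 6/7, after 24 hours of observation (Study Plans and Procedures). Readmission is at 23 0/7 and the latest planned delivery at 34 0/7 (Methods). I take the window as unbroken from consent to its end.

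**Gestational age in days** (7 × weeks + days): 18 0/7 = 126; 18 1/7 = 127; 22 6/7 = 160; 23 0/7 = 161; 34 0/7 = 238.

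**The protocol's own figure.** The recruitment flyer gives a maximum of 16 weeks in the study: 238 − 126 = 112 days = 16 weeks. It reproduces.

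**Stop day, treated arm, full course.** The last dose falls on day 6 if the first dose is counted as day 0, or day 7 if counted as day 1. Stop = 6 + 30 = 36 or 7 + 30 = 37.

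| | Randomised 18 1/7 (127) | Randomised 22 6/7 (160) |
|---|---|---|
| Window closes | 163-164 = 23 2/7 to 23 3/7 | 196-197 = 28 0/7 to 28 1/7 |
| Days past readmission (161) | 2-3 | 35-36 |
| Days from closure to 34 0/7 (238) | 74-75 | 41-42 |
| Randomisation to 34 0/7 | 238 − 127 = 111 | 238 − 160 = 78 |
| Share covered | 36/111 to 37/111 = 32-33% | 36/78 to 37/78 = 46-47% |

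The uncovered stretch is therefore 41 to 75 days when pregnancy reaches 34 0/7, and shorter otherwise. Placing the late entrant at 23 0/7 (rupture at 22 6/7 plus a day of observation) shifts these results by one day.

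**Where the gap lies.** After a full course the window always runs past 23 0/7, so the planned outpatient phase is covered and the gap is in the inpatient phase. Early stopping changes this only at the lower edge. Randomised at 127 and stopped on day 0, the window closes at 127 + 30 = 157 = 22 3/7; stopped on day 3, at 160 = 22 6/7. Randomised at 130 (18 4/7) and stopped on day 0, it closes at 160 = 22 6/7; from 131 onward it reaches at least 161 = 23 0/7.

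**Controls.** There is no date of last dose, so no stop day can be computed. If the opening sentence of section 1A governs, all SAEs are collected with no end. If the second sentence governs, the end is undefined. Neither reading gives day 36-37.

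**The case against.** The best defence is that section 1A opens with a duty that has no drug anchor and no end date. Where the 30-day clause cannot apply, that duty plausibly remains, so controls are covered in full. This is a fair reading, and it defeats the inference that SAEs in controls go uncollected. It does not make the windows equal: controls would then be followed longer than treated women.

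Late reporting is also not empty. Events related to a procedure in the protocol stay reportable in both arms, and readmission care is laid down for both. Appendix IV records chorioamnionitis and endomyometritis with no day limit. Both points stand. Neither requires an SAE report for a late event judged unrelated to drug and procedure.

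One might instead start the control clock at the antibiotics given to both arms at 23 0/7. Those are described as standard care, controls who deliver earlier would still have no date, and the two arms would run on different clocks.

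A reader might also infer three stronger points that the document does not support:
- Section 2A says "The collection of nonserious AE information should begin at initiation of study drug", which could suggest that controls' nonserious events are lost. Its next sentence extends collection to a baseline observational period, dosing begins straight after randomisation, and the section sets no dosing-based stop.
- Safety Assessments lists adverse event incidence but fixes no window, so section 1A does not contradict it.
- Appendix IV has no dedicated field for some fetal and neonatal outcomes. That is separate from the stop date. The sheet has ultrasound reports and discharge summaries filed, and other case report pages are not shown.

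**Conclusion.** The point holds as a conflict between section 1A and Ethical and Regulatory Requirements. The all-cause SAE window ends about day 36-37 in treated women who complete the course, and has no matching end for the 17 of 34 who are controls. The adverse event definition, tied to a subject given a product, has the same flaw.

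The size is bounded. The 41 to 75 uncovered days are maxima that require pregnancy to reach 34 0/7; they are not an expected gap. A woman who delivers by about day 37 has no gap before delivery. The protocol gives no latency distribution, so the share of pregnancies beyond day 37 is unknown. The latency and viability endpoints are unaffected. What is at risk is a like-for-like SAE comparison and complete reporting in the longest treated pregnancies. That merits correction without calling the efficacy analysis into question. The figures assume a full seven-day course begun at randomisation.

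**What to change.** Define an adverse event for any randomised subject, whether or not a product was given. Collect all SAEs in both arms from consent, through delivery, to one fixed postpartum point, regardless of relatedness. Amend Adverse Event Procedures and section 1A so that both agree with Ethical and Regulatory Requirements.

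The cost is amendment wording, approved in advance by both review boards as the Protocol requires, and slightly longer data collection in 34 pregnancies. No treatment or visit rule changes.

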## 2. Nonserious Adverse Events

A nonserious adverse event is an AE not classified as serious.

### 2A. Nonserious Adverse Event Collection and Reporting

The collection of nonserious AE information should begin at initiation of study drug. Non-serious AE information should also be collected from the start of a placebo lead-in period or other observational period intended to establish a baseline status for the subjects.

Nonserious AEs should be followed to resolution or stabilization, or reported as SAEs if they become serious (see Section 1A). Follow-up is also required for nonserious AEs that cause interruption or discontinuation of study drug and for those present at the end of study treatment as appropriate. All identified nonserious AEs must be recorded and described on the nonserious AE page of the CRF.

Completion of supplemental CRFs may be requested for AEs and/or laboratory abnormalities that are reported/identified during the course of the study.

### 3. Laboratory Test Result Abnormalities

The following laboratory test result abnormalities should be captured on the nonserious AE CRF page or SAE Report Form as appropriate:

- Any laboratory test result that is clinically significant or meets the definition of an SAE
- Any laboratory test result abnormality that required the subject to have study drug discontinued or interrupted
- Any laboratory test result abnormality that required the subject to receive specific corrective therapy.

It is expected that wherever possible, the clinical rather than laboratory term would be used by the reporting investigator (e.g., anemia versus low hemoglobin value).

### 4. Overdose

An overdose is defined as the accidental or intentional administration of any dose of a product that is considered both excessive and medically important. All occurrences of overdose must be reported as an SAE (see Section 1A for reporting details.).

5. Potential Drug Induced Liver Injury (DILI)

Wherever possible, timely confirmation of initial liver-related laboratory abnormalities should occur prior to the reporting of a potential DILI event. All occurrences of potential DILIs, meeting the defined criteria, must be reported as SAEs (see Section 1A for reporting details).

Potential drug induced liver injury is defined as:

AT (ALT or AST) elevation > 3 times upper limit of normal (ULN)

AND

Total bilirubin > 2 times ULN, without initial findings of cholestasis (elevated serum alkaline phosphatase),

AND

No other immediately apparent possible causes of AT elevation and hyperbilirubinemia, including, but not limited to, viral hepatitis, pre-existing chronic or acute liver disease, or the administration of other drug(s) known to be hepatotoxic.

6. Other Safety Considerations

Any significant worsening noted during interim or final physical examinations, electrocardiogram, x-ray filming, any other potential safety assessment required or not required by protocol should also be recorded as a nonserious or serious AE, as appropriate.

**Discontinuations**

The reason for a subject discontinuing from the study will be recorded in the patient chart. A discontinuation occurs when an enrolled subject ceases participation in the study, regardless of the circumstances, prior to completion of the protocol. The investigator must determine the primary reason for discontinuation. Withdrawal due to adverse event will be distinguished from withdrawal due to insufficient response according to the definition of adverse event noted earlier. The investigator will record the reason for study discontinuation, provide or arrange for appropriate follow-up (if required) for such subjects, and document the course of the subject's condition. They will also to be reported to

Woman's Hospital Foundation Institutional Review Board at [contact], Woman's Health Research Institute at [contact], and LSUHSC Institutional Review Board.

Subjects MUST discontinue investigational product for any of the following reasons:

- Withdrawal of informed consent (subject's decision to withdraw for any reason).
- Any clinical adverse event, laboratory abnormality, or intercurrent illness, which, in the opinion of the investigator, indicates that continued participation in the study is not in the best interest of the subject.
- Loss of ability to freely provide consent through imprisonment or involuntary incarceration for treatment of either a psychiatric or physical (e.g., infectious disease) illness.

All subjects who discontinue should comply with protocol-specified follow-up procedure. The only exception to this requirement is when a subject withdraws consent for all study procedures or loses the ability to consent freely (i.e., is imprisoned or involuntarily incarcerated for the treatment of either a psychiatric or physical illness).

Perform physical examination.

Patient excluded from enrollment

- 1) Visualization of amniotic fluid passing from the cervical canal and pooling in the vagina via sterile speculum examination
- 2) A basic pH denoted by positive nitrazine testing of vaginal fluid
- 3) Arborization (ferning) of dried vaginal fluid (dry time of 10min) identified via microscopic examination
- 4) Amniotic fluid index (AFI) less than 4cm

Positive for one or more findings

None of the findings noted on exam

Overnight admission for 24hr observation period.\*  
Implement "PRETERM PREMATURE RUPTURE OF MEMBRANES" Clinical Pathway: Select "PPROM STUDY PROTOCOL" within order set.

Patient excluded from enrollment

Page24

24hr observation period

**NO TYLENOL OR IBUPROFEN TO BE GIVEN DURING 24HR OBSERVATION PERIOD.**

Laboring, febrile, vaginal bleeding, non-reassuring fetal status based on sonographic imaging

Yes to any

Patient excluded from enrollment

No to all  
Version 1.0

Randomization into treatment (antibiotic) and control (no antibiotic) arms

\* *HRU Admit: afebrile, no vaginal bleeding, cervical dilation ≤2cm, ≤4 contractions/hr on tocometry*  
*L&D Admit: do not meet HRU criteria*

